3.1.2.2 Treatment Period

From **Visit 2** onward, all visits will be the same for all patients regardless of whether they were considered to be "naïve" or "non-naïve" at the time of screening.

During the treatment period, all patients will receive N-Acetyl-L-Leucine for 42 days (+7 days). Visit 3 (Treatment 1) will occur at Day 28 (+7 days) of the treatment period and Visit 4 (Treatment 2) will occur after the full 42 days (+7 days) of treatment.

3.1.2.3 Washout Period

A 42-day (+7 days) washout period will be performed following treatment with N-Acetyl-L-Leucine. **Visit 5** (Washout 1) will occur on Day 28 (+7 days) of the washout period and **Visit 6** (Washout 2) will occur after the full 42 days (+7 days) of washout.

3.1.2.4 Extension Phase

Patients who have participated in the study will be offered the opportunity to participate in a planned Extension Phase if the safety and tolerability during the 42-day (+7 days) treatment are considered to be acceptable by the Investigator for each specific patient, and the Investigator determines further treatment with IB1001 to be in the patient's interest. Provided the patient (or their legal representative on their behalf) subsequently consent to participate, the Extension Phase is planned to allow patients to have further access to IB1001 for one year. Following a 6-week post Extension Phase treatment washout (Visit 10 of the Extension Phase), patients will have further access to IB1001 for an additional one-year in the Extension Phase Treatment Period II.

See Appendix 6 for the Protocol for Extension Phase.

3.1.2.5 COVID-19 Modifications to the Original Study Schema

COVID-19 has significantly impacted study subjects' ability to attend study visits due to government-ordered lockdowns or the closure of state (domestic) and/or national borders. In addition, the issuance of site-specific policies limiting or halting the conduct of non-essential study visits, the conversion of study-sites into COVID-19 wards, and site staff not on duty or reassigned to other priorities at the hospitals have affected the feasibility of conducting study visits. Finally, considering GM2 patients are already classified as a vulnerable patient population, patients may be self-isolating.

If, per the reasons above, in-person visits cannot be carried out in accordance with the schedule of events, the following departures from the original study schema are allowed:

3.1.2.5.1 Non-Essential In-Person Visits: Treatment Visit 3/ Washout Visit 5

- Visit 3 and Visit 5 are "interim" visits of the treatment and washout phases, respectively.
- The Sponsor's Medical Expert, Medical Monitor, the DSMB, Biostatistician and Principal Investigators consider that missing the in-person Visit 3 and / or Visit 5 would not compromise the safety of the patient or the integrity of the study, and that the patient could continue with medication (Visit 3) or the post-treatment washout phase (Visit 5) without attending the in-person Visit 3 and / or Visit 5. This risk assessment was based on the previously established safety profile of IB1001 (see Section 1), the observed very good tolerability shown to date in this ongoing, open-

label study, including that no related serious adverse reactions had been reported with IB1001 (in any ongoing trial), that these visits are not critical to the primary outcome assessment, and that the integrity of the clinical trial could be maintained if these visits were not performed due COVID-19 restrictions.

- Therefore, in-person Visit 3 and Visit 5 have been classified as non-essential visits and may be skipped if they are not feasible to conduct in-person due to national, local, or site-specific restrictions, or necessary to safeguard the site staff, patients, and their families. If the in-person Visit 3 and / or Visit 5 is skipped, a remote visit should be conducted in lieu of the in-person visit (see Section 3.1.2.5.3 below).

3.1.2.5.2 Essential In-Person Visits: End of Treatment Visit 4/ Washout Visit 6

- Visit 4 and Visit 6 are the final visits of the treatment/washout phase (respectively)
- The Sponsor's Medical Expert, Medical Monitor, the DSMB, and each Principal Investigator determined that the in-person Visit 4 and Visit 6 are necessary visits needed to fully assess the safety of trial participants, the primary endpoint, and maintain the integrity of the clinical trial.
- However, it was determined (if they are not feasible to conduct in-person due to national, local, or site-specific restrictions, or necessary to safeguard the site staff, patients, and their families) postponing the in-person Visit 4 and/or Visit 6 would not compromise the safety of the patient, and that the patient could continue with medication / be dosed longer than the planned 42 days (+7 days) treatment period (Visit 4). This risk assessment was based on the previously established safety profile of IB1001 (see Section 1), the observed good tolerability shown to date in this ongoing, open-label study, including that no related serious adverse reactions had been reported with IB1001 (in any ongoing clinical trial), that the Extension Phase (including one-year treatment period with IB1001) had been approved in all countries, and that data collected from these postponed in-person Visit 4 and/or Visit 6 was acceptable for the purpose of assessing a true treatment-related effect.
- Therefore, Visit 4 and Visit 6 have been classified as essential study visits which may be postponed (if they are not feasible to conduct in-person due to national, local, or site-specific restrictions, or necessary to safeguard the site staff, patients, and their families) but cannot be skipped. If Visit 4 and / or Visit 6 is postponed, a remote visit should be conducted at the time of the original the in-person visit (see Section 3.1.2.5.3 below)

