8.5.1 Primary Efficacy Endpoint

The primary endpoint for the study is based on blinded raters' Clinical Impression of Change in Severity (CI-CS) comparing videos showing the patient's change in performance over 42 days (+7 days) on a pre-defined anchor clinical symptom scale: either the 9 Hole Peg Test of the Dominant Hand (9HPT-D) or the 8 Meter Walk Test (8MWT). A manual will be provided to each clinical site, which provides instructions for the administration of the CI-CS [Fields, 2020]. Similarly, a video-acquisition manual will be provided, which provides instructions for making standardized videos of the 8MWT and 9HPT-D primary anchor tests The comparison of the Visit 4 video with the Visit 2 video and the comparison of the Visit 6 video with the Visit 4 video will provide the scores that contribute to the primary endpoint. Each of these comparisons will score change on a 7-point Likert scale (+3=significantly improved to -3= significantly worse).

During the pre-treatment period, the treating physician will evaluate each patient's clinical symptoms and select, at **Visit 1**, either the 9HPT-D or 8MWT as the primary anchor around which the CI-CS assessment will be scored. A cognitive assessment should be performed at **Visit 1** according to standard procedures of the clinical site to assist with the selection of the anchoring functional test appropriate for each patient from both a cognitive and a motor perspective.

The primary evaluation of the CI-CS will be performed by two independent raters whose assessments will be based on videos of the anchor test taken at each visit. These raters will be blinded to the treatment periods (baseline, treatment, or washout) to reduce detection and performance bias.

The primary endpoint is defined as the CI-CS comparing end of treatment with N-Acetyl-L-Leucine (Visit 4) with baseline (Visit 2) minus the CI-CS comparing the end of washout (Visit 6) with the end of treatment with N-Acetyl-L-Leucine (Visit 4) based on the primary anchor test.

The CI-CS assessment will instruct the blinded rater to consider: 'compared to the first video, how has the severity of their performance on the 9HPT-D or 8MWT changed (improved or worsened) in 6-weeks as observed in the second video?'

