8.10 Determination of Sample Size

It is postulated that N-Acetyl-L-Leucine will show effectiveness in 30% of patients and this success rate is viewed as being clinically important. Assuming that this group of patients will have scores that are evenly distributed across the values 1 and 2 for the primary endpoint and further that the remaining 70% of patients will have scores that are evenly distributed between the values -1, 0, and 1. The resulting mean score is 0.45 and the standard deviation (SD) for the primary endpoint under these assumptions is then 1.02. With 30 patients reporting on the primary endpoint, the study will have 76% power to detect a treatment benefit in a 5% one-sided one-sample t-test.

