5.6.1 Primary endpoint

The primary efficacy endpoint is based on the blinded raters' Clinical Impression of Change in Severity (CI-CS) score over 6 weeks determined by comparing videos showing the patient's performance on a pre-defined anchor clinical symptom scale: either the 9 Hole Peg Test of the Dominant Hand (9HPT-D) or the 8 Meter Walk Test (8MWT).

For each patient, there will be two CI-CS scores. These two scores indicate the level of change in severity observed in Visit 4 (end of treatment) compared to Visit 2 (baseline) and the level of change in severity observed in Visit 6 (end of washout) compared to Visit 4 (end of treatment). Both CI-CS scores are measured on a 7-point Likert-point scale (-3 = significantly worse to +3 = significantly improved, see Section 5.2 for the precise definition) and the primary endpoint is defined as the difference between both CI-CS scores.

The primary endpoint will be summarized using descriptive statistics, including a frequency table, and frequency percentages will be presented graphically using a bar chart. The primary statistical analysis will be performed using a one-sample t-test comparing the CI-CS difference score to zero. Statistical output will present the number of patients included in the analysis, both CI-CS scores, the mean of the difference, the corresponding two-sided 90% confidence interval, and a one-sided p-value.

The assumption of normality will be visually checked and if the assumption does not hold, a Wilcoxon signed-rank test will be performed instead of the t-test using the difference score. Statistical output will then present the number of patients included in the analysis, both CI-CS scores, the (pseudo-) median of the difference using the Hodges-Lehmann estimator, the corresponding two-sided 90% confidence interval, and a one-sided p-value.

Clinical Study Reference: IB1001-202

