8 COVID-19 DETAILS

This study is conducted during the COVID-19 outbreak. The following data capture decisions have been taken due to national, local, or site-specific restrictions imposed due to COVID-19, with the primary need to prioritize the safety of clinical study teams and patients, and to maintain the integrity of the study/data collection.

- All protocol deviations relating to COVID-19 are collected.
- If Visit 2 is performed 8 weeks (56 days) or more after Visit 1, some Visit 1 assessments must be repeated.
- Visits 3 and 5 can be converted to remote visits (i.e. phone, video conference).
- Visits 4 and 6 can be postponed until the in-person visit is feasible and should be performed in person. Where applicable, remote data collection should be collected on the date of the original visit. The postponed Visits 4 and 6 will collect all data per protocol.
- For the Extension Phase, no remote visits are allowed.

Currently, the impact of COVID-19 on the proposed statistical analyses is unknown. The statistical analysis already allows some flexibility for handling missing data, however, specific items/changes related to COVID-19 are being detailed in a separate document (Addendum 1), which will be maintained as a living document throughout the study continuation and adjusted based on the duration and extent of the impact of the COVID-19 situation.

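### The primary endpoint cancels steady progression only if treatment and washout are equally long, yet Visits 4 and 6 may be postponed and the supplied plan has no analysis for unequal intervals

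*Protocol*

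**What the plan says.** Protocol 8.5.1 takes the CI-CS for Visit 4 against Visit 2, "minus the CI-CS comparing the end of washout (Visit 6) with the end of treatment". SAP 5.6.1 analyses this with a "one-sample t-test comparing the CI-CS difference score to zero", in the mITT set (SAP 5.6). Protocol 5.2 confirms a single arm with no comparator. Treatment and washout are each planned at 42 days, with a window of +7 days (Protocol 3.1.2.2 and 3.1.2.3).

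Protocol 3.1.2.5 lets an in-person Visit 4 or Visit 6 be postponed, but not skipped, where COVID-19 restrictions or safeguarding require it. It gives as one reason that "data collected from these postponed in-person Visit 4 and/or Visit 6 was acceptable for the purpose of assessing a true treatment-related effect". SAP section 8 says: "Visits 4 and 6 can be postponed until the in-person visit is feasible and should be performed in person". Neither text states a maximum delay. The remote contact at the planned date is not to be video-recorded, and the later in-person visit is entered as Visit 4 or Visit 6 (Protocol 3.1.2.5.3), so the late video is the one scored. If Visit 4 is late, dosing continues until it takes place (Protocol 5.3).

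The wording of the endpoint stays at six weeks. SAP 5.6.1 describes a "score over 6 weeks determined by comparing videos", and the rater's question in Protocol 8.5.1 asks how performance has "changed (improved or worsened) in 6-weeks as observed in the second video".

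**The concern.** With no control arm, the design relies on symmetry between the on-drug and off-drug periods to remove natural decline. Protocol 8.5.1 counts deterioration after withdrawal as part of the drug effect, so any extra decline in a prolonged washout is scored as benefit. Extra decline in a prolonged treatment period is scored against the drug.

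Progression is the sponsor's own premise. The Protocol introduction describes deterioration, and section 8.5.1 of the Extension Phase appendix postulates that 90% of patients worsen on the mDRS over 12 months under standard of care.

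The supplied text has no safeguard for the primary test. Its only sensitivity analysis concerns missing washout videos (Protocol 8.6, SAP 5.6). The SAP handles COVID-19 delay for adverse events through patient-years (SAP 5.7.1) and sets a 56-day rule for the gap between Visits 1 and 2 (SAP section 8). It has no counterpart for the two intervals that form the primary endpoint. What is at stake is both the false-positive rate and the power of the primary test.

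**Working it through.** **Inputs from the documents.** One-sided 5% one-sample t-test; mean 0.45, SD 1.02 and n=30 (Protocol 8.10); about 36 patients in the mITT set (Protocol 3.1.3).

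**Inputs that are assumptions.** The rate of natural decline on the CI-CS scale, the length of delays and the share of patients delayed. The documents give none of these.

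**Step 1: the plan's own figures.** Protocol 8.10 puts 15% of patients at each of 1 and 2, and 23.3% at each of −1, 0 and 1.
- Mean = 0.15 × 1 + 0.15 × 2 + 0 = 0.45.
- Variance = (0.15 × 1 + 0.15 × 4 + 0.2333 × 2) − 0.45² = 1.2167 − 0.2025 = 1.0142. The SD is therefore 1.007, or 1.024 with an n−1 divisor at n=30.

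This agrees with "The resulting mean score is 0.45 and the standard deviation (SD) for the primary endpoint under these assumptions is then 1.02". With noncentrality 0.45/1.02 × √30 = 2.416 on 29 degrees of freedom, the noncentral t gives power of 76.3%, which agrees with "the study will have 76% power to detect a treatment benefit in a 5% one-sided one-sample t-test".

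**Step 2: expected endpoint with an inert drug.** Let s be the natural worsening in points per week.
- CI-CS over treatment: −s × T1
- CI-CS over washout: −s × T2
- Endpoint: −s × T1 − (−s × T2) = s × (T2 − T1)

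This is zero when T1 = T2, including when both are prolonged equally. It is positive when T2 exceeds T1 and negative when T1 exceeds T2.

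**Step 3: size under assumed values.** If only Visit 6 is late, mean bias = (decline per 6 weeks) × (delay in weeks / 6) × (share delayed). A 12-week delay in 25% of patients gives:
- decline of 0.1 per 6 weeks: 0.1 × 2 × 0.25 = 0.05
- decline of 0.3 per 6 weeks: 0.3 × 2 × 0.25 = 0.15

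These are 11% and 33% of the planned mean (0.05/0.45 and 0.15/0.45).

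**Step 4: rejection rates with no drug effect.** The mean bias is put into the Step 1 test with SD 1.02.

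| Mean bias | n=30 | n=36 |
|---|---|---|
| 0 | 5.0% | 5.0% |
| +0.05 | 8.3% | 8.7% |
| +0.10 | 13.1% | 14.3% |
| +0.15 | 19.5% | 21.8% |
| −0.10 | 1.5% | 1.3% |

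A simulation with scores rounded to the −3 to +3 scale, run for biases including +0.10 and −0.10 at n=30, agreed within one percentage point.

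**Step 5: the reverse direction.** A bias of −0.10 arises, for example, if every patient has 84 days of treatment and 42 of washout, with an assumed decline of 0.10 per 42 days. A true mean of 0.45 is then seen as 0.35, and power at n=30 falls from 76% to 58%.

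**The case against.** The strongest objection is that the remedy may already exist. Protocol 8.11 and SAP section 8 assign COVID-19 changes to SAP Addendum 1, which was not available for this review. A rule on intervals would naturally sit there. This stands: the finding is that no such analysis is visible in the supplied text, not that the sponsor has none.

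A reader might infer that the primary result is biased in favour of the drug. The documents do not support that. A late Visit 4 works against the drug, equal delays cancel, and nothing shows which visit was delayed more often or by how much.

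A reader might also infer that postponement is unlimited. It is conditional on restrictions or safeguarding and lasts only until an in-person visit is feasible, and Protocol 10.4 allows alternative locations. What can be said is that no maximum is stated.

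The illustrated sizes rest on assumptions. A decline of 0.3 per 6 weeks extrapolates to 0.3 × 52/6 = 2.6 points a year on a change scale that ends at −3, so the upper end is demanding. At 0.1 the rejection rate in the example is 8%, against a nominal 5%.

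Some mitigation exists. Delayed assessments are listed as protocol deviations (Protocol 8.1.1), and a PPS analysis is planned. However, major or minor status is decided at the data review meeting (SAP 3.4), and exclusion would affect only the PPS, not the primary mITT test.

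The fixed six-week wording in the rater's question does not cause the bias. It may also help to protect the blind, since disclosing true intervals could reveal which pair was delayed. No change to it is needed.

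**Conclusion.** The point holds as a gap in the supplied analysis plan. The primary endpoint removes steady progression only when T1 = T2. The COVID-19 rules allow T1 and T2 to differ with no stated maximum, and the mITT test uses the late videos without adjustment or a sensitivity analysis. The Protocol's statement that postponed data are acceptable comes with no supporting analysis.

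The bias can run either way, and neither its size nor its net direction can be determined from the documents. The rejection rates of 8% to 20% at n=30 and 9% to 22% at n=36, for a mean bias of 0.05 to 0.15, are illustrations. They assume linear decline, no drug effect and SD 1.02. So does the fall to about 1.5% at n=30 for a bias of −0.10. None of these is an estimate for this trial.

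The sponsor should make this change. Confidence is moderate, because Addendum 1 was not available and the delays are unknown.

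**What to change.** If Addendum 1 already covers unequal intervals, cross-reference it in SAP 5.6.1. Otherwise add to SAP 5.6.1 two prespecified supportive analyses of the primary endpoint in the mITT set, using the visit dates already collected:

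1. The same test restricted to patients whose V2–V4 and V4–V6 intervals both lie within 42 (+7) days. A difference of up to 7 days remains possible, worth 0.1 × 7/42 = 0.017 to 0.3 × 7/42 = 0.05 under the assumed decline rates.
2. An estimate adjusted for T2 − T1, such as a regression whose intercept is the effect at equal intervals. Describe it as exploratory if few patients were delayed.

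Tabulate T1, T2 and T2 − T1. Actual visit dates per patient are already to be listed (SAP 5.8.1 and Listing 16.2.4.3), so this is a derivation rather than new data. Interpret the primary result alongside both analyses. A formal rule barring an efficacy conclusion is not proposed: Protocol 8.2 uses significance only as a guide in this Phase II trial.

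The cost is one SAP paragraph and one table. The restricted analysis will be smaller and less precise, and the regression slope may be poorly estimated with about 36 patients. The primary test itself is unchanged.

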3.1.2.5.3 Remote Visits

For any (i) skipped in-person Visit 3/5; (ii) postponed in-person Visit 4/6: based on the availability of the patient/ the study team, within approximately +/- 3 days of the originally scheduled visit, the study team/ principal investigator (PI) should contact the patient (and as applicable, their parents/caregiver/legal representative) via phone/Skype⁵ to collect information in order to monitor adverse or serious adverse events, and provide study oversight (hereafter referred to as "**remote visits**").

Assessments which may be able to be performed remotely (as feasible) may include:

- Documentation of (changes in) frequency of therapy (hours per week)
- Documentation of (changes in) concomitant medication

⁵ As feasible; Skype is used as a generic term for videoconferencing, telemedicine but other software's may be used. No video recordings should be made of these remote visits.

- Quality of Life EQ-5D-5L for patients aged ≥18 years, EQ-5D-Y for patients aged <18 years
- Clinical Global Impression of Severity (CGI-S)
- Clinical Global Impression of Change (CGI-C)
- Documentation of changes in or new adverse events / serious adverse events
- Discuss if additional study drug is needed (V3 only)
- PATA Speech Test
- Modified Disability Rating Scale
- Scale for the Assessment and Rating of Ataxia
- Additional Protocol Assessments which the Investigator/ Patient mutually agree to perform/assess

Assessments collected at a remote Visits 3 and/or Visit 5 should be entered into the electronic case report form (eCRF) under Visit 3 and/or Visit 5.

Assessments collected from remote Visit 4 and/or Visit 6 should be entered into eCRF as an Unscheduled Visit. When the postponed, in-person Visit 4 and/or Visit 6 is performed, all assessments collected at this visit should be entered into the eCRF as Visit 4 and/or Visit 6.

See Section 9.5 for additional information on how contingency measures/protocol deviations related to COVID-19 will be captured in the electronic case report form (eCRF)/ documented in the Parent Study Clinical Study Report (CSR).

3.1.2.6. Interim Analyses

No interim analyses are planned throughout the Parent Study.

At the end of the Parent Study (defined as the date of the last visit of the last patient in the Parent Study globally; see Section 3.3 End of Study Definition) an interim clinical study report will be written which will include the results of the Parent Study.

3.1.3 Target Number of Patients

- To be enrolled: Approximately 39 patients
- To be analyzed according to the modified Intention to Treat (mITT) analysis: Approximately 36 patients
- To be analyzed according to the Per Protocol Analysis: Approximately 30 patients

3.1.4 Number of Centers

The trial will be conducted in a total of approximately 8 centers in the United States, the United Kingdom, Germany, or Spain, which must meet the structural and personnel requirements for performing the planned regular trial-related investigations.

If necessary, additional countries may be included in the trial.

